5.9 UNSCHEDULED VISIT

An unscheduled visit may be performed at any time during the study at the patient's request or as deemed necessary by the investigator. The date and reason for the unscheduled visit will be recorded. AE monitoring and concomitant medication recording should be performed. Appropriate procedures and evaluations will be completed as deemed necessary by the investigator and may include (but are not limited to) laboratory tests, vital signs and physical examination.

Corticosteroid use may be managed at a scheduled visit, unscheduled visit, or phone call followup based on investigator discretion.

5.10 PHONE CALL FOLLOW-UP

Systemic corticosteroid usage may be managed at a scheduled visit, unscheduled visit, or phone call follow-up per the discretion of the investigator. If a phone call follow-up for corticosteroid use management is performed, other concomitant treatment and AE data should also be collected.

5.11 POST TREATMENT PHONE CALL

Approximately 2 and 4 months after Visit 8 (Day 84), a follow-up phone call will be placed and the following assessments will be performed: completion of ABQOL questionnaire, adverse event assessment, and concomitant medication reporting. Corticosteroid usage (oral and topical) will be documented and managed as necessary.

6.0 INVESTIGATIONAL PRODUCT

6.1 IDENTITY OF INVESTIGATIONAL PRODUCT

Bertilimumab is a recombinant human IgG4 monoclonal antibody that neutralizes human eotaxin-1 (eotaxin); the drug product consists of bertilimumab formulated in phosphate buffered saline (PBS) at pH 7.2 and at a concentration of 10 mg/mL, presented as a sterile, clear, colorless solution in 10 mL clear glass vials.

The formula for the PBS is sodium chloride 77 mM, monosodium phosphate 17 mM and disodium phosphate 50 mM.

6.2 STUDY DRUG ADMINISTRATION AND DOSAGE

Bertilimumab 10 mg/kg will be administered by IV over 30 minutes of infusion time. The weight used for dose calculation at all dosing days is the weight measured at screening.

6.3 MANUFACTURING OF STUDY MEDICATION

Patheon UK and Nova Laboratories Ltd, cGMP vendors, will perform the drug product manufacturing and release.

6.4 PACKAGING AND LABELLING OF STUDY MEDICATION

Bertilimumab vials will be packaged and labeled in compliance with GCP and local health authority guidelines.

Site designee(s) will be responsible for handling and preparation of the study test medication.

Refer to the IP Manual for more details.

6.5 DISTRIBUTION AND SHIPMENT OF STUDY MEDICATION

The patients' investigational drug supplies will be packed and shipped in appropriate boxes. If, upon arrival at the clinical investigation site, study drug supplies appear to be damaged, the study monitor should be contacted immediately.

Each shipment of study drug supplies for the study will be accompanied by a shipment form describing the contents of the shipment, acknowledgement of receipt and other appropriate documentation. The shipment form will assist in maintaining current and accurate inventory records. The study staff will confirm the receipt of clinical supply to the study monitor.

6.6 STORAGE AND INSTRUCTIONS FOR PREPARATION AND INFUSION OF THE INVESTIGATIONAL PRODUCT

The study medication will be stored at each site under refrigeration at 2-8°C.

Records should be kept by the designee(s) as to how much study drug was used by each patient. The study monitors must periodically check the study drug supplied to ensure expiry date and sufficient amount of study drug, ensure that drug accountability is being performed at each visit and that drug accountability logs are maintained.

All investigational products must be kept in a locked area with access to the study drug limited to designated study personnel.

Preparation of the study drug dose for administration must be carried out by a trained medical professional at the study center using aseptic technique according to the Pharmacy Manual. The number of vials used as well as the study drug volume dispensed per dose will be recorded in the study logbook. Instructions for preparation and administration of study drug are detailed in the IP Manual.

Only trained personnel are authorized to prepare and administer study drug to participating patients.

6.7 ACCOUNTABILITY AND COMPLIANCE OF INVESTIGATIONAL PRODUCT

Each delivery must be acknowledged by the study team member responsible for the investigational medicinal product by filling in the receipt record form and returned according to the instructions included in the IP shipment. Accurate, complete, and timely documentation for all distribution to the study staff and patients will be maintained by the site designee(s), which may include confirmation of receipts of clinical supply, drug accountability logs and other forms.

The site designee(s) is responsible for ensuring the supervision of the storage and allocation of these supplies, which will be forwarded to the investigator or designee at the appropriate time

before administration. Investigational drug will be administered only to patients who meet the eligibility criteria of the study.

Drug accountability records must be maintained by the clinical investigation site at all times. All used and unused investigational drug will be collected and drug accountability performed by the site designee(s). The study monitor will check these regularly during monitoring visits.

Unused drug supplies will be returned to the Sponsor, unless instructed otherwise. At the end of the study, all the clinical supply and the corresponding accountability forms must be returned to the Sponsor, the study monitor or designee for reconciliation and destruction. A photocopy of these records must be kept at the clinical investigation site.

The inventory will be made available to the study monitor who will verify accountability and verify dose during the course of the study.

Study drug orders, records of study drug receipts, dispensing records, and inventory forms located at the site will be examined and reconciled by the study monitor periodically during and at the end of the study.

6.8 CONCOMITANT THERAPY

At the screening visit, relevant treatments currently received by the patient will be recorded in the patient's file and on the patient's CRF including treatment name, indication, dose, total daily dose, and start and stop dates.

Any medications (including prescription, over-the-counter, herbal supplements, and other health store-type products) to be taken during the study must be recorded in the CRF. All concomitant medications used to treat AEs will also be recorded.

6.8.1 Concomitant Corticosteroid Therapy

• Newly diagnosed patients:

Due to the potential effects of long-term and/or high-dose systemic corticosteroid usage on bullous pemphigoid, patients will be permitted to take systemic oral corticosteroids specifically for bullous pemphigoid only for a period of 4 weeks prior to the first treatment administration (Visit 2 - Day 0) at doses no greater than 40 mg/day prednisone equivalent.

Patients who have taken systemic oral corticosteroid for bullous pemphigoid longer than 4 weeks prior to the first treatment administration (Visit 2 - Day 0) or at doses greater than 40 mg/day prednisone equivalent at any time are excluded from the study.

For patients who have used systemic corticosteroids for reasons other than bullous pemphigoid, a washout period of 4 weeks prior to the first treatment administration (Visit 2 - Day 0) is required.

For patients who are taking systemic oral corticosteroids at a daily dose between 40 mg/day and 30 mg/day prednisone equivalent for BP within 4 weeks prior to the first treatment administration (Visit 2 - Day 0), tapering of systemic corticosteroids is to be conducted at the discretion of the investigator. However, patients must be on 30 mg/day prednisone equivalent for the first treatment administration (Visit 2 - Day 0). For patients who are taking less than 30 mg/day prednisone equivalent prior to the first administration day (Visit 2 - Day 0), a stable dose of systemic corticosteroids should be maintained until Visit 2 (Day 0).

Patients resistant to corticosteroid tapering:

No wash-out period is required.

The tapering schedule depicted in Table 1 is recommended for the remainder of the study.

Table 1: Recommended Corticosteroid Tapering Regimen

Systemic corticosteroid dose (prednisone equivalent) per day	Tapering schedule
≥30.0-10.1 mg/day	Decrease by 5 mg each week
$10.0-0~\mathrm{mg/day}$	Decrease by 2.5 mg each week

Corticosteroid management can occur either during a scheduled visit, unscheduled visit, or phonecall follow-up per the investigator's discretion.

Table 2: Corticosteroid Comparison Chart

	Approximate Equivalent Dose, mg	Relative Potency
Cortisol	20	1.0
Cortisone	25	0.8
Prednisone	5	4.0
Prednisolone	5	4.0
Triamcinolone	4	5.0
Dexamethasone	0.75	30-150

Reference: Welsh GA, Manzullo EF and Nieman LK The surgical patient taking glucocorticoids. 2007 UpToDate® www.uptodate.com.

On completion of the study, patients will be treated according to local practice and at the investigator's discretion.

Other corticosteroid regimens other than those listed in Table 2 are permitted only if the patient is considered, in the opinion of the investigator, unable to taper down corticosteroid treatment. No wash-out period is required.

6.8.2 Rescue Therapy

If necessary, rescue therapy is permitted at any point during the study at the discretion of the investigator. The patient can continue in the study as long as the rescue therapy is clearly documented.

6.8.3 Prohibited Prior and Concomitant Medication

Medications having the potential to interfere with the study assessments are excluded throughout the trial and include:

- Systemic corticosteroids administered for reasons other than bullous pemphigoid without a washout period of 4 weeks prior to the first treatment administration (Visit 2 - Day 0) or at any time during the study for newly diagnosed patients.
- Systemic corticosteroids taken specifically for bullous pemphigoid at any dose (greater than 40 mg/day prednisone equivalent) within 4 weeks prior to the first treatment administration day (Visit 2 - Day 0) or greater than 40 mg/day prednisone equivalent at any time prior to the first treatment administration day or at any time during the study for newly diagnosed patients
- Treatment with class 1 and 2 topical steroids within 2 weeks prior to the first treatment administration day (Visit 2 – Day 0) or at any time during the study for newly diagnosed patients
- Immunosuppressive drugs (e.g., methotrexate, azathioprine, mycophenolate mofetil, dapsone) within 4 weeks prior to the first treatment administration day (Visit 2 Day 0) or at any time during the study
- Biological therapies (e.g., intravenous Ig, etanercept, adalimumab, ustekinumab, infliximab) within 4 months and rituximab within 1 year prior to the first treatment administration day (Visit 2 Day 0) or at any time during the study
- Treatment with a full course of macrolides or tetracyclines within 4 weeks prior to the first treatment administration day (Visit 2 Day 0) or at any time during the study
- Use of vaccines or other immunostimulator within 4 weeks prior to the first treatment administration day (Visit 2 Day 0) or at any time during the study

In the interests of patient safety and acceptable standards of medical care, the investigator may prescribe additional treatment(s) at his/her discretion, which will be recorded on the patient's CRF.

7.0 SAFETY AND PHARMACOVIGILANCE

7.1 ADVERSE EVENT

An adverse event (AE) is any untoward medical occurrence in a patient or clinical investigation subjectand which does not necessarily have to have a causal relationship with this treatment. This includes any subjective signs, symptoms or diagnosis, clinically significant deviation from baseline screening laboratory values or vital signs, or worsening (more severe, more frequent or increased in duration during the investigational product treatment) of the concomitant disease present at Visit 2 (Day 0) visit (after initiation of investigational product treatment). Stable chronic conditions that are present prior to study entry and do not worsen during the study will not be considered AEs. Disease-related adverse events will not be considered AEs unless they worsen beyond what would be expected in the normal progression of the disease. In all cases, the etiology should, as much as possible, be identified and the Sponsor notified.

An abnormal result of diagnostic procedures including abnormal laboratory or vital sign findings will be considered an AE if it:

- Results in patient's withdrawal by the investigator
- Is associated with clinical signs or symptoms

Is considered by the physician to be of clinical significance.

Adverse events reported by the patient or observed by the investigator will be individually listed on an AE form in the CRF as follows: the specific event or condition, whether the event was present pre-study, the dates and times of occurrence, duration, severity, likelihood of relationship to study medication, specific countermeasures, and outcome.

The intensity or severity of the AE will be characterized as:

Mild: Transient or mild discomfort; no limitation in activity; no medical

intervention/therapy required

Moderate: Mild to moderate limitation in activity - some assistance may be needed;

no or minimal medical intervention/therapy required

Severe: Marked limitation in activity, some assistance usually required; medical

intervention/therapy required; hospitalization possible

The Investigator will document his/her opinion regarding the relationship of the AE to the investigational product (study medication) using the following criteria:

Category	Definition
Unrelated	Clearly due only to extraneous causes, and does not meet criteria listed under possible or probable.
Unlikely	Does not follow a reasonable temporal sequence from administration. May have been produced by the patient's clinical state or by environmental factors or other therapies administered.
Possible	Follows a reasonable temporal sequence from administration, but may have been also produced by the patient's clinical state, environmental factors or other therapies administered.
Probable	Clear-cut temporal association with administration with improvement on cessation of investigational medicinal product or reduction in dose. Reappears upon rechallenge. Follows a known pattern of response to the investigational medicinal product.

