5.3.7 Safety Laboratory Assessments

Safety laboratory assessments will be performed according to the Schedule of Events (Appendix A).

Hematology and Biochemistry will be performed at all visits with the exception of Visits 6 (Day 56), 7 (Day 70), and 9 (Day 118) as indicated in the Schedule of Events (Appendix A). At treatment administration Visits 2 (Day 0), 3 (Day 14), and 4 (Day 28), these samples will be taken pre-dose (any time prior to the initiation of treatment infusion). For screening, hematology and chemistry will be evaluated locally and at a central laboratory for all other visits.

Serology will be evaluated locally only at Screening.

Pregnancy will be evaluated locally by serum at Screening and locally by urine testing at all other visits with the exception of Visits 6 (Day 56) and 7 (Day 70).

Anti-bertilimumab antibodies will be evaluated at all visits with the exception of screening and Visit 9 (Day 118). At treatment administration Visits 2 (Day 0), 3 (Day 14), and 4 (Day 28), antibertilumamb samples will be collected pre-dose (any time prior to the initiation of treatment infusion). Anti-bertilumamb antibodies will be evaluated centrally.

The following parameters will be tested for each assessment:

Evaluations Parameters

Hematology Hematocrit, hemoglobin, platelet count, red blood cell count, reticulocytes, white

blood cell count with differential count, monocytes

Biochemistry Alanine aminotransferase, alkaline phosphatase, aspartate aminotransferase,

calcium, cholesterol, creatinine, gamma-glutamyl transferase, glucose, potassium,

sodium, total bilirubin, triglycerides, urea or BUN

Immunology Anti-bertilimumab antibodies

Pregnancy test Serum β-hCG

Urine β-hCG

Serology For HBV (HBsAg or HBcAb), HCV (HCV Ab), HIV (HIV1/2 Ab), CMV (IgM)

All laboratory tests with abnormal values which are considered clinically significant and are detected after the informed consent is signed will be repeated as clinically indicated until the values return to normal, or until the etiology has been determined and the condition considered stable. Abnormal laboratory test results that are considered clinically important by the investigator will be reported as an AE in the AE CRF.

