### **Hematology / Chemistry**

All hematology and chemistry tests will be divided into the following categories based on the normal ranges provided by the sites:

- ✓ Clinically significant below the normal range (CS below)
- ✓ Non-clinically significant below the normal range (NCS below)
- ✓ Within the normal range (Normal)
- ✓ Non-clinically significant above the normal range (NCS above)
- ✓ Clinically significant above the normal range (CS above)

  Note: The above is relevant for all tests where the normal ranges are applicable.
- By-test and by-subject listing of Hematology/ Chemistry results across visits.
   Note: The results will be presented using the above categories, where CS results will be highlighted. Screening data will not be presented as it was collected by separate local labs for screening purposes only and is, thus, not comparable to other rest results analyzed centrally (at one US and one Israeli central lab).
- By-subject listing of clinically significant abnormal hematology / urinalysis results.

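### Protocol 7.1 measures laboratory AEs against Screening values that the SAP treats as not comparable; the Visit 2 pre-dose sample should be the reference for post-dose changes

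*Protocol*

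**What the plan says.** The AE definition in Protocol 7.1 covers "clinically significant deviation from baseline screening laboratory values or vital signs". The same sentence uses a different reference for comorbidity, namely worsening "of the concomitant disease present at Visit 2 (Day 0) visit (after initiation of investigational product treatment").

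Protocol 5.3.7 fixes where the tests are run: "For screening, hematology and chemistry will be evaluated locally and at a central laboratory for all other visits". Footnote e of Appendix A agrees. Section 5.3.7 also schedules a pre-dose sample at Visit 2, so a central pre-treatment value is planned for every patient.

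SAP 9.3.2 (Hematology / Chemistry) leaves the Screening data out of its listing because they were "collected by separate local labs for screening purposes only and is, thus, not comparable to other rest results analyzed centrally".

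Elsewhere Day 0 is the baseline. The synopsis and Appendix A label Visit 2 that way. SAP 6.2.2, under the Efficacy population, takes the last value before treatment. The Vital Signs part of SAP 9.3.2 measures change at Visits 5 to 8 from the Visit 2 pre-dose reading.

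**The concern.** The plan asks sites to judge a laboratory change against results that its own analysis will not use. Two things other than bertilimumab can separate a Screening result from a later one: the change of laboratory, and whatever happens to the patient before Day 0. The second is foreseeable. Screening can last 28 days, Protocol 6.8.1 allows newly diagnosed patients up to 40 mg/day prednisone equivalent in that time, and the synopsis says corticosteroid use is managed during screening.

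AEs head the list of primary safety endpoints in Protocol 2.2, with no limit on relatedness or onset. SAP 9.3.2 gives only listings for hematology and chemistry (the blood eosinophil count is summarized separately as a PD endpoint). The AE tables are thus almost the only tabulated summary of laboratory safety, and a misdated laboratory AE has no change-from-baseline table beside it to expose the error.

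**Working it through.** The plan states no AE rate, power or sample-size justification, so there is no figure to reproduce. The check is mainly a comparison of passages.

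**1. Which reference applies where**

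| Place | Reference |
|---|---|
| Protocol 7.1, laboratory values and vital signs | Screening |
| Protocol 7.1, concomitant disease | Visit 2 (Day 0) |
| Synopsis and Appendix A, label for baseline | Day 0 |
| SAP 6.2.2 | Last value before treatment |
| SAP 9.3.2, vital signs at Visits 5 to 8 | Visit 2 pre-dose |
| SAP 9.3.2, hematology and chemistry listing | Screening omitted |

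The laboratory clause of 7.1 is the outlier. Its wording is also ambiguous, since it joins the word for baseline to Screening while other sections attach baseline to Day 0.

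**2. How a pre-treatment difference could become a post-dose AE**

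Take a patient with local Screening value A, central Visit 2 pre-dose value B, and B again at Visit 3.
- Against Screening, the Visit 3 change is B − A, which mixes the laboratory difference with any pre-treatment shift.
- Against Visit 2 pre-dose, it is B − B = 0.

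If the site calls B − A clinically significant and first records it at Visit 3, the onset falls after the first infusion and meets the SAP 7.1.2 definition of treatment-emergent. No section says how to date a change first recorded at Visit 3 but already visible in the Visit 2 pre-dose sample. For physical examination, Protocol 5.3.5 sends findings present before study drug to medical history. Section 5.3.7 has no matching rule for laboratory findings and covers whatever is detected after consent.

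**3. Where the AE would then appear**

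- Protocol 2.2 primary endpoint: yes, without condition.
- SAP 9.3.2 tables of all AEs: yes. No treatment-emergent restriction is written there, although SAP 7.1.2 defines the term.
- SAP 7.1.1 main safety endpoints: only if rated possibly or probably related, or if serious.

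**4. Size**

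With up to 15 patients, one patient is 1/15 = 6.7 percentage points of incidence.

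The chance of at least one such patient depends on a rate that the documents do not give. As an illustration only, let p be an assumed chance, per patient and parameter, that a spurious change is called clinically significant. Protocol 5.3.7 names 7 hematology and 13 biochemistry parameters, 20 in all. Treating them as independent:

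P(at least one of 15 patients) = 1 − (1 − p)^(20 × 15) = 1 − (1 − p)^300

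| Assumed p | P(at least one patient) |
|---|---|
| 0.05% | 14% |
| 0.1% | 26% |
| 0.2% | 45% |
| 0.5% | 78% |
| 1% | 95% |

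Positive correlation between parameters would lower these figures. A range from 14% to 95% shows that the size cannot be settled from the documents.

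**The case against.** The best defense is that Screening is not the only yardstick, and that other safeguards do most of the work.

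- The quoted clause is one illustration within a broad AE definition. Section 7.1 then gives a separate rule for abnormal results: withdrawal, signs or symptoms, or that the result "Is considered by the physician to be of clinical significance". That rule names no reference visit, and 5.3.7 likewise rests on the investigator's judgment.
- The AE form records "whether the event was present pre-study, the dates and times of occurrence".
- A laboratory difference or steroid effect should first show in the Visit 2 pre-dose sample, so a careful site would date it before treatment.

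Most of this stands. A reader might infer that a change of laboratory by itself generates AEs. It does not, because each route needs clinical significance, symptoms or withdrawal. A reader might also infer that a harmful on-drug return toward the Screening value would be barred as an AE. It would not, because the separate rule still admits it.

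The safeguards do not close the gap completely. Judgment needs a reference, and the only one that 7.1 names for laboratory change is Screening. The onset rule is missing, and a Day 0 onset recorded by date alone is ambiguous. The relatedness condition is a modest filter, because the possible category in 7.1 needs only a reasonable time sequence even where another therapy may be the cause.

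Two further readings go beyond the text. The non-comparability statement covers hematology and chemistry, not vital signs. And the phrase "more severe, more frequent or increased in duration during the investigational product treatment" might suggest that comorbidity worsening after the last infusion is lost. The documents do not support that: the definition's list is not exhaustive, 5.3.1 and Appendix A collect AEs at every visit and follow-up call, and 7.1 excludes stable chronic conditions only if they "do not worsen during the study will not be considered AEs".

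**Conclusion.** The conflict is real and should be corrected: Protocol 7.1 points laboratory AEs to Screening values that the SAP will not use, although a suitable central pre-dose sample is already scheduled. A laboratory difference or pre-treatment shift could enter the primary AE endpoint as a post-dose event. This requires that the site applies the Screening reference, judges the change clinically significant, and first records it at Visit 3 or later.

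How often that would happen is unknown. Each such patient moves incidence by 6.7 percentage points if 15 are treated. The documents do not support a claim that the SAP's main safety results are distorted as a matter of course, because such an event reaches them only if rated related or serious. For vital signs the point is consistency with SAP 9.3.2 only.

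**What to change.** 1. **Protocol 7.1.** Name the Visit 2 (Day 0) pre-dose value, from the central laboratory for hematology and biochemistry, as the reference for post-dose laboratory changes. Use the Visit 2 pre-dose reading for vital signs as well, in line with SAP 9.3.2. Keep Screening values for eligibility and for pre-treatment events.
2. **Onset rule.** State that a change already present in the Visit 2 pre-dose sample has a pre-treatment onset and is not treatment-emergent.
3. **SAP 9.3.2, Adverse Events.** Add tables restricted to treatment-emergent AEs as defined in SAP 7.1.2. Changing the reference alone would not do this, since AE collection starts at consent and the all-AE tables include pre-dose events.
4. **If data collection is complete**, as SAP 7.4 suggests when it mentions a decision taken after the study ended, apply the rule in the analysis by flagging each recorded laboratory AE against the Visit 2 pre-dose value.

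**Cost.** No new samples or visits. A change to 7.1 is a protocol modification and needs submission under Protocol 9.3, plus revised AE instructions at up to 10 sites; the analysis route needs only SAP text and programming. One small downside: a patient with no Day 0 central result has no reference and must be flagged.

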7.2 SERIOUS ADVERSE EVENT

A **serious** adverse event (SAE) is any adverse event occurring after signing informed consent at any dose that suggests a significant hazard or side effect, regardless of the investigator or sponsor's opinion on the relationship to the investigational product and that results in, but may not be limited to, any of the following outcomes:

- Death (regardless of the cause)
- Life-threatening adverse drug experience
- Inpatient hospitalization or prolongation of existing hospitalization (any inpatient hospital admission that includes a minimum of an overnight stay in a health care facility)
- Persistent or significant disability/incapacity
- Congenital anomaly or birth defect.

Important medical events that may not be fatal, life threatening, or require hospitalization may be **serious** when, based upon appropriate medical judgment, they may jeopardize the patient and may require medical or surgical intervention to prevent one of the outcomes listed above.

Hospitalization for elective treatment of a pre-study condition that did not worsen while on study and hospitalizations for treatment of non-adverse events (e.g., cosmetic surgery) are not considered serious adverse events. Situations where an untoward medical occurrence did not occur (e.g., social and/or convenience admission to a hospital) are not considered as serious adverse events.

The underlying medical condition for any surgery performed should be reported as the event term rather than the procedure itself.

Significant medical events are those which may not be immediately life threatening, but may jeopardize the patient and may require intervention to prevent one of the other serious outcomes listed above. Examples of such events are intensive treatment in an emergency room or at home for allergic bronchospasm; blood dyscrasias or convulsions that do not result in hospitalization; resulting in an adverse event which would normally be considered serious by this criterion.

Inpatient hospitalization or prolongation of existing hospitalization refers to hospital inpatient admission and/or prolongation of hospital stay required for treatment of AE, or which occurred as a consequence of the event. Hospitalization for elective treatment of a pre-study condition that did not worsen while on study and hospitalizations for treatment of non-adverse events (e.g., cosmetic surgery or diagnostic procedure) are not considered serious adverse events.

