### **Serious Adverse Events (SAEs):**

All SAEs will be tabulated using frequency tables with - Number of Subjects and Percentage of Subjects by:

- Overall by System Organ Class (SOC), Preferred Term and maximal severity
- Overall by System Organ Class (SOC), Preferred Term and maximal relation to study drug
- By subject listing of SAEs

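### The undefined normal-progression exclusion in Protocol 7.1 carries over into the SAE definition in 7.2, so an admission for a pemphigoid flare can be missing from the AE and SAE tables

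*Protocol*

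**What the plan says.** Protocol 7.1 contains an exclusion: "Disease-related adverse events will not be considered AEs unless they worsen beyond what would be expected in the normal progression of the disease". It offers no threshold, time frame or adjudication step. The same paragraph counts as an AE any worsening "of the concomitant disease present at Visit 2 (Day 0) visit", without saying whether BP itself is meant.

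Protocol 7.2 says that an SAE "is any adverse event occurring after signing informed consent at any dose that suggests a significant hazard or side effect" and that has one of the listed outcomes. The hospitalisation outcome carries the gloss "any inpatient hospital admission that includes a minimum of an overnight stay in a health care facility". A later paragraph of 7.2 narrows this to an admission or longer stay "required for treatment of AE, or which occurred as a consequence of the event". It also sets aside elective treatment of a pre-study condition that has not worsened, and admissions for things that are not adverse events. Social or convenience admissions are set aside elsewhere in 7.2.

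SAP 7.1.1 makes SAEs a main safety endpoint. SAP 9.3.1 provides that "All SAEs will be tabulated using frequency tables" by number and percentage of subjects. Flares are placed among the additional efficacy endpoints (SAP 7.2.2 and 9.4.2). They are taken from the header of the BPDAI/pruritus form and, like all efficacy analyses, are run on the Efficacy population.

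**The concern.** Protocol 1.3 presents the study as a test of whether steroids can be tapered faster than physicians are used to, and it ties efficacy in taper-resistant patients to tapering without a flare. Section 4.5.1 foresees flares. Worsening BP, and admission for it, is therefore a foreseeable harm of the strategy under study.

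Whether such an event counts depends on an open-label judgement of what was to be expected. The exclusion works in one direction only: it can leave the count of AEs and SAEs unchanged or lower it, but never raise it. Two sites could also classify the same flare admission differently and both be following the protocol, which would make the SAE percentage hard to interpret. The 24-hour notification in Protocol 7.4 depends on the same classification.

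**Working it through.** The plan states no SAE rate, interval or power figure, so there is nothing of its own to reproduce. The check is to follow one case through the text: a patient has a BP flare after dosing and is admitted overnight for it.

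| Step | Reading A: flare judged within expected progression | Reading B: flare treated as worsened disease |
|---|---|---|
| Protocol 7.1 | The exclusion applies, so it is not an AE | The clause on worsening of a disease present at Visit 2 applies, or the flare exceeds expectation, so it is an AE |
| Protocol 7.2, definition | Not an AE, so it cannot be an SAE | An AE with an overnight admission, so it is an SAE |
| Protocol 7.2, hospitalisation text | Admission for a non-adverse event, set aside | The elective exemption covers only conditions that did not worsen, so it does not apply |
| SAP 9.3.1 and 9.3.2 | Absent from SAE and AE tables | Present in both |

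Both columns can be defended from the text, and nothing in either document chooses between them.

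Next, could another planned output recover the admission under Reading A?

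- Corticosteroid and concomitant medication listings (SAP 9.3.2, Safety population) may show a dose increase or rescue treatment, but not an admission.
- Physical examination tables and listings (SAP 9.3.2) may show a skin finding, but not an admission.
- BPDAI and prednisone summaries (SAP 9.4.1) may show worsening by visit, but not an admission.
- The flare table (SAP 9.4.2) covers patients with a baseline and at least one later BPDAI (SAP 6.2.2). The schedule has no BPDAI at Visit 9 or at the phone calls around Days 144 and 204, so a flare first noted then has no flare record. AE reporting remains the main route, and the exclusion applies to it.
- The general CRF listings (SAP 10) show whatever was entered. Neither document describes a separate CRF record of hospital admissions.

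Size, for illustration only. Inputs: n = 15, the planned maximum in the Protocol synopsis, assumed all treated; x = number of patients with an SAE. Exact (Clopper-Pearson) 95% limits:

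- Lower limit: 0 if x = 0, otherwise the 2.5% quantile of Beta(x, n − x + 1).
- Upper limit: the 97.5% quantile of Beta(x + 1, n − x). For x = 0 this is 1 − 0.025^(1/n).

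Results:

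- Weight of one patient: 1/15 = 6.7 percentage points.
- 0/15: 0%, upper limit 1 − 0.025^(1/15) = 21.8%.
- 1/15: 6.7% (0.2 to 31.9%).
- If only 10 patients were treated: 0/10 is 0% (0 to 30.8%) and 1/10 is 10.0% (0.3 to 44.5%).

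**The case against.** The strongest case against is that the sections can be read together and that the gap is narrow. Section 7.1 does not exclude all disease-related events. Those worse than expected stay in, and a flare bad enough for admission may well qualify. The Severe grade in 7.1 itself mentions possible hospitalisation. The SAP leaves other traces of worsening, the Protocol synopsis plans individual patient narratives, and the Efficacy population may differ little from the Safety population. The analysis is descriptive, with no planned interval or test on the SAE rate. All of this stands. It limits how often the gap would matter, but it does not close it.

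A reader might also infer that 7.2 makes every inpatient admission serious whatever its cause, so that the two sections conflict head-on and give two different SAE rates. The documents do not support that. The phrase "regardless of the investigator or sponsor's opinion on the relationship to the investigational product" concerns attribution to the product, not the reason for admission. Indifference to cause is attached to one outcome only: "Death (regardless of the cause)". Because 7.2 requires an adverse event first, a flare excluded under 7.1 is excluded under 7.2 as well, and one classification gives one count. The problem is an inherited, undefined exclusion alongside wording that invites the opposite reading.

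Nor do the documents show that any admission was in fact left out. They show only that it could be.

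**Conclusion.** The point holds in this limited form. An admission for a BP flare that the investigator regards as expected can be missing from the AE and SAE tables of a study whose primary objective is safety, and no planned output is designed to reveal it. This rests on the absence of any criterion for expected progression, on SAEs being defined as a subset of AEs, and on the lack of a control arm. The direction is known: any effect lowers the reported count. The frequency is not known, since the documents give no number of flare admissions. The 6.7-point figure is the weight of one patient if 15 are treated, not an estimate of bias. The matter should be corrected because it touches a main safety endpoint and costs little to put right.

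**What to change.** Protocol, or any successor protocol: reconcile 7.1 and 7.2. Restrict the disease-related exclusion to events that meet no seriousness criterion in 7.2. State that any BP worsening that does meet one is recorded as both an AE and an SAE, whatever the view on expected progression. Say whether the clause on concomitant disease at Visit 2 includes BP. This changes how events are recorded, not how patients are managed.

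SAP: the note on ECP and IgE in Section 7.4 indicates that the study had already been completed, so new protocol wording cannot alter what sites entered. In Section 9.3, add a supplementary listing on the Safety population, labelled as such, of all recorded hospitalisations and flares whatever their AE status. Show SAEs with and without BP-related admissions. Where a recorded admission for BP was not reported as an SAE, query the investigator rather than recode it centrally. Steroid increases and rescue use should not be turned into SAEs, because neither is a seriousness criterion in 7.2.

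Cost: a little extra listing work and some site queries. The listing can hold only what sites noted, and the SAE rate may look less favourable.
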